## Stryker Neurovascular

**Document Title:** Trevo® Retriever Registry (China) Statistical Analysis Plan

**Document Number:** CDM10001420

**Ver AA**

Range (min, max)	xx.x (xx.x, xx.x)
Stroke symptom onset to reperfusion	
Mean ± SD (N)	xx.x ± xx.x (xxx)
Median (Q1, Q3)	xx.x (xx.x, xx.x)
Range (min, max)	xx.x (xx.x, xx.x)
Time of clot integration	
Mean ± SD (N)	xx.x ± xx.x (xxx)
Median (Q1, Q3)	xx.x (xx.x, xx.x)
Range (min, max)	xx.x (xx.x, xx.x)

\*: Time intervals may be reported but not limited to those listed in the table. It will subject to change as needed.

STRYKER CONFIDENTIAL - THIS DOCUMENT CONTAINS CONFIDENTIAL AND PROPRIETARY INFORMATION THAT IS THE PROPERTY OF STRYKER CORPORATION. NEITHER THIS DOCUMENT NOR THE INFORMATION HEREIN MAY BE REPRODUCED, USED, OR DISCLOSED TO ANY THIRD PARTY WITHOUT THE PRIOR WRITTEN CONSENT OF STRYKER CORPORATION

## Stryker Neurovascular

**Document Title:** Trevo® Retriever Registry (China) Statistical Analysis Plan

**Document Number:** CDM10001420

**Ver AA**

**Table 7: Modified Rankin Scale (mRS)**

Modified Rankin Scale (mRS)	% (n/N)
Pre-Stroke (N=xxx)	
0	xx.x% (xx/xxx)
1	xx.x% (xx/xxx)
2	xx.x% (xx/xxx)
Discharge/Day 5-7 (whichever comes first) (N=xxx)	
0	xx.x% (xx/xxx)
1	xx.x% (xx/xxx)
2	xx.x% (xx/xxx)
3	xx.x% (xx/xxx)
4	xx.x% (xx/xxx)
5	xx.x% (xx/xxx)
6	xx.x% (xx/xxx)
0-2 combined	xx.x% (xx/xxx)
Day 30	
0	xx.x% (xx/xxx)
1	xx.x% (xx/xxx)
2	xx.x% (xx/xxx)
3	xx.x% (xx/xxx)
4	xx.x% (xx/xxx)
5	xx.x% (xx/xxx)
6	xx.x% (xx/xxx)
0-2 Combined	xx.x% (xx/xxx)
Day 90	
0	xx.x% (xx/xxx)
1	xx.x% (xx/xxx)
2	xx.x% (xx/xxx)
3	xx.x% (xx/xxx)
4	xx.x% (xx/xxx)
5	xx.x% (xx/xxx)
6	xx.x% (xx/xxx)
0-2 Combined	xx.x% (xx/xxx)

STRYKER CONFIDENTIAL - THIS DOCUMENT CONTAINS CONFIDENTIAL AND PROPRIETARY INFORMATION THAT IS THE PROPERTY OF STRYKER CORPORATION. NEITHER THIS DOCUMENT NOR THE INFORMATION HEREIN MAY BE REPRODUCED, USED, OR DISCLOSED TO ANY THIRD PARTY WITHOUT THE PRIOR WRITTEN CONSENT OF STRYKER CORPORATION

## Stryker Neurovascular

**Document Title:** Trevo® Retriever Registry (China) Statistical Analysis Plan

**Document Number:** CDM10001420

**Ver AA**

**Table 8: Summary of NIH Stroke Scale (NIHSS)**

NIH Stroke Scale (NIHSS)	Number of Subjects (N=xxx)
Pre-procedure	
Mean $\pm$ SD (N)	xx.x $\pm$ xx.x (xxx)
Median (Q1, Q3)	xx.x (xx.x, xx.x)
Range (min, max)	xx.x (xx.x, xx.x)
24(-6/+24) post procedure	
Mean $\pm$ SD (N)	xx.x $\pm$ xx.x (xxx)
Median (Q1, Q3)	xx.x (xx.x, xx.x)
Range (min, max)	xx.x (xx.x, xx.x)
Discharge/Day 5-7 (whichever comes first)	
Mean $\pm$ SD (N)	xx.x $\pm$ xx.x (xxx)
Median (Q1, Q3)	xx.x (xx.x, xx.x)
Range (min, max)	xx.x (xx.x, xx.x)

STRYKER CONFIDENTIAL - THIS DOCUMENT CONTAINS CONFIDENTIAL AND PROPRIETARY INFORMATION THAT IS THE PROPERTY OF STRYKER CORPORATION. NEITHER THIS DOCUMENT NOR THE INFORMATION HEREIN MAY BE REPRODUCED, USED, OR DISCLOSED TO ANY THIRD PARTY WITHOUT THE PRIOR WRITTEN CONSENT OF STRYKER CORPORATION

## Stryker Neurovascular

**Document Title:** Trevo® Retriever Registry (China) Statistical Analysis Plan

**Document Number:** CDM10001420

**Ver AA**

**Table 9: Recanalization Results**

Modified TICI	% (n/N)
Subjects in Pre-procedure (N=xxx)	
0	xx.x% (xx/xxx)
1	xx.x% (xx/xxx)
2a	xx.x% (xx/xxx)
2b	xx.x% (xx/xxx)
3	xx.x% (xx/xxx)
2b+	xx.x% (xx/xxx)
Subjects at the end of each pass* (N=xxx)	
0	xx.x% (xx/xxx)
1	xx.x% (xx/xxx)
2a	xx.x% (xx/xxx)
2b	xx.x% (xx/xxx)
3	xx.x% (xx/xxx)
2b+	xx.x% (xx/xxx)
Subjects at the end of procedure (N=xxx)	
0	xx.x% (xx/xxx)
1	xx.x% (xx/xxx)
2a	xx.x% (xx/xxx)
2b	xx.x% (xx/xxx)
3	xx.x% (xx/xxx)
2b+	xx.x% (xx/xxx)

\*: mTICI from all passes (up-to 6) need to be reported.

**Table 10: Primary endpoint**

mTICI 2b+ at the end of procedure	% of subjects with mTICI2b+	95%CI
Yes	xx.x% (xx/xxx)	(xx.x%, xx.x%)

STRYKER CONFIDENTIAL - THIS DOCUMENT CONTAINS CONFIDENTIAL AND PROPRIETARY INFORMATION THAT IS THE PROPERTY OF STRYKER CORPORATION. NEITHER THIS DOCUMENT NOR THE INFORMATION HEREIN MAY BE REPRODUCED, USED, OR DISCLOSED TO ANY THIRD PARTY WITHOUT THE PRIOR WRITTEN CONSENT OF STRYKER CORPORATION

## Stryker Neurovascular

**Document Title:** Trevo® Retriever Registry (China) Statistical Analysis Plan

**Document Number:** CDM10001420

**Ver AA**

**Table 11: Secondary endpoints**

Secondary Endpoints	% of Subjects with Clinical Outcomes (n/N)*
mRS** of 0-2 at Day 90	xx.x% (xx/xxx)
Mortality rate at Day 90	xx.x% (xx/xxx)
Neurological deterioration at 24(-6/+24) hours	xx.x% (xx/xxx)
Study Device and procedure related SAE	xx.x% (xx/xxx)

\*:95% CI will be generated as needed for ad hoc analysis  
\*\*: LOCF is used for Day 90 mRS.

STRYKER CONFIDENTIAL - THIS DOCUMENT CONTAINS CONFIDENTIAL AND PROPRIETARY INFORMATION THAT IS THE PROPERTY OF STRYKER CORPORATION. NEITHER THIS DOCUMENT NOR THE INFORMATION HEREIN MAY BE REPRODUCED, USED, OR DISCLOSED TO ANY THIRD PARTY WITHOUT THE PRIOR WRITTEN CONSENT OF STRYKER CORPORATION

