**Ver AA**

4. Rate of study device and procedure related serious adverse events (SAE) through Day 90.

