**Ver AA**

**Table 12: All SAEs**

	# of events	Percentages of subjects with events* (Total subjects=xxx)
All SAEs		
Details of all SAEs	xx	xx.x% (xx/xxx)
...	xx	
...	xx	xx.x% (xx/xxx)
...	xx	xx.x% (xx/xxx)
Study device and procedure related SAEs		
Total	xx	xx.x% (xx/xxx)
Details of study device and procedure related SAEs	xx	xx.x% (xx/xxx)
...	xx	xx.x% (xx/xxx)
...	xx	xx.x% (xx/xxx)
...	xx	xx.x% (xx/xxx)
Study device related SAEs only		
Total	xx	xx.x% (xx/xxx)
Details of study device related SAEs	xx	xx.x% (xx/xxx)
...	xx	xx.x% (xx/xxx)
...	xx	xx.x% (xx/xxx)
...	xx	xx.x% (xx/xxx)
Procedure but not study device related SAEs		
Total	xx	xx.x% (xx/xxx)
Details of procedure but not study device related SAEs	xx	xx.x% (xx/xxx)
...	xx	xx.x% (xx/xxx)
...	xx	xx.x% (xx/xxx)
...	xx	xx.x% (xx/xxx)
Study device or procedure related SAEs		
Total	xx	xx.x% (xx/xxx)
Details of study device or procedure related SAEs	xx	xx.x% (xx/xxx)
...	xx	xx.x% (xx/xxx)
...	xx	xx.x% (xx/xxx)
Not study device and not procedure related SAEs		
Total	xx	xx.x% (xx/xxx)
Details of not study device and not procedure related SAEs	xx	xx.x% (xx/xxx)
...	xx	xx.x% (xx/xxx)
...	xx	xx.x% (xx/xxx)

\*: Some subjects may experience multiple events

STRYKER CONFIDENTIAL - THIS DOCUMENT CONTAINS CONFIDENTIAL AND PROPRIETARY INFORMATION THAT IS THE PROPERTY OF STRYKER CORPORATION. NEITHER THIS DOCUMENT NOR THE INFORMATION HEREIN MAY BE REPRODUCED, USED, OR DISCLOSED TO ANY THIRD PARTY WITHOUT THE PRIOR WRITTEN CONSENT OF STRYKER CORPORATION

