**Ver AA**

**Table 13: All AEs during procedure**

	# of events	Percentages of subjects with events* (N=xxx)
Total AEs	xx	xx.x% (xx/xxx)
Details of AEs during procedure	xx	xx.x% (xx/xxx)
...	xx	xx.x% (xx/xxx)
...	xx	xx.x% (xx/xxx)
...	xx	xx.x% (xx/xxx)
Study device and procedure related AEs		
Total	xx	xx.x% (xx/xxx)
Details of study device and procedure related SAE	xx	xx.x% (xx/xxx)
...	xx	xx.x% (xx/xxx)
...	xx	xx.x% (xx/xxx)
...	xx	xx.x% (xx/xxx)
Study device related AEs		
Total	xx	xx.x% (xx/xxx)
Details of study device related AEs	xx	xx.x% (xx/xxx)
...	xx	xx.x% (xx/xxx)
...	xx	xx.x% (xx/xxx)
...	xx	xx.x% (xx/xxx)
Procedure but not study device related AEs		
Total	xx	xx.x% (xx/xxx)
Details of procedure but not study device related AEs	xx	xx.x% (xx/xxx)
...	xx	xx.x% (xx/xxx)
...	xx	xx.x% (xx/xxx)
...	xx	xx.x% (xx/xxx)
Study device or procedure related AEs		
Total	xx	xx.x% (xx/xxx)
Details study device or procedure related AEs	xx	xx.x% (xx/xxx)
...	xx	xx.x% (xx/xxx)
...	xx	xx.x% (xx/xxx)
Not study device and not procedure related AEs		
Total	xx	xx.x% (xx/xxx)
Details of not study device and not procedure related SAEs	xx	xx.x% (xx/xxx)
...	xx	xx.x% (xx/xxx)
...	xx	xx.x% (xx/xxx)

\*: Some subjects may experience multiple events

STRYKER CONFIDENTIAL - THIS DOCUMENT CONTAINS CONFIDENTIAL AND PROPRIETARY INFORMATION THAT IS THE PROPERTY OF STRYKER CORPORATION. NEITHER THIS DOCUMENT NOR THE INFORMATION HEREIN MAY BE REPRODUCED, USED, OR DISCLOSED TO ANY THIRD PARTY WITHOUT THE PRIOR WRITTEN CONSENT OF STRYKER CORPORATION

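### The related-SAE endpoint row in SAP Table 11 carries the label that Table 12 uses for events related to both device and procedure, so it could leave out SAEs related to only one of them

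*SAP*

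**What the plan says.** SAP 5.2.2, item 4, defines the fourth secondary endpoint as "Rate of study device and procedure related serious adverse events (SAE) through Day 90". Table 11 gives it one row, "Study Device and procedure related SAE", as a percentage of subjects. So the window and the unit of counting are stated. How the two relatedness judgements combine is not.

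Table 12 breaks SAEs down by relatedness under these block headings:

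- "Study device and procedure related SAEs"
- "Study device related SAEs only"
- "Procedure but not study device related SAEs"
- "Study device or procedure related SAEs"
- a last block for SAEs related to neither.

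Table 13 does much the same for AEs during the procedure, starting with "Study device and procedure related AEs".

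Protocol 5.2 and SAP 2.2.2 also join device and procedure with *and*, but speak of rates in the plural. Under Protocol 14.2 the investigator judges the relationship to the device and to the procedure separately, so an SAE can be related to one and not the other.

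**The concern.** The Table 11 label and the first relatedness label in Table 12 match apart from a capital letter and the plural. A programmer who fills the endpoint row from the block of the same name would report only subjects with an SAE attributed to both sources. A programmer who reads the endpoint as either source would report the combined block. Both could claim to follow the SAP, and the figures would differ.

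The error can go in one direction only. Subjects with an SAE related to both are a subset of those with an SAE related to either, so the literal reading gives an equal or lower rate. This row is the registry's secondary endpoint on harm from the device and procedure, and an endpoint table may be quoted without the table that follows it.

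**Working it through.** **Step 1: what the Table 12 label means.** The table never prints the word *both*, so the meaning has to come from the layout. Suppose *and* meant either source. The first block would then repeat "Study device or procedure related SAEs" and one of the two would be redundant. Suppose instead it means related to both. Then the *and*, *only* and *but not* blocks divide the *or* block into three parts, with the neither block completing the table. Only the second reading gives every block a purpose.

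**Step 2: does other text settle the endpoint?** SAP 5.2.2, SAP 2.2.2 and Protocol 5.2 all use *and* without saying either or both. SAP 5.2.2 has a singular rate and Table 11 one row; SAP 2.2.2 and Protocol 5.2 have the plural, which may mean two separate rates. Three readings remain open: both, either, or two rates.

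**Step 3: size.** The plan gives no expected rate for this endpoint, so there is no figure to reproduce. The only counts available are from the TREVO study (Protocol 2.1, Table 2): device-related SAEs D = 3 and procedure-related SAEs P = 5, with N = 60. Assumptions: these are subject counts, and a subject in both counts had an SAE related to both sources. The number shared, k, is not reported, so the range 0 to 3 is shown.

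- Row filled from the *and* block: k/60
- Row filled from the *or* block: (D + P − k)/60 = (8 − k)/60
- Omitted: (8 − 2k)/60

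| k | *and* block | *or* block | Omitted | Scaled to 200 subjects, *and* vs *or* |
|---|---|---|---|---|
| 3 (fully nested) | 3/60 = 5.0% | 5/60 = 8.3% | 2/60 = 3.3% | 10.0 vs 16.7 |
| 2 | 2/60 = 3.3% | 6/60 = 10.0% | 4/60 = 6.7% | 6.7 vs 20.0 |
| 1 | 1/60 = 1.7% | 7/60 = 11.7% | 6/60 = 10.0% | 3.3 vs 23.3 |
| 0 | 0/60 = 0.0% | 8/60 = 13.3% | 8/60 = 13.3% | 0.0 vs 26.7 |

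Full nesting gives the smallest gap these counts allow. In that case both omitted subjects are procedure-only.

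Single-source events are realistic. Protocol 2.1 describes three symptomatic haemorrhages in TREVO and contrasts one classed as device-related with two classed as procedure-related.

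**The case against.** The strongest counter-argument is that the protocol shows what was meant. Protocol 14 asks for SAEs attributed to the device or to the procedure up to Day 90, and Protocol 8.4 to 8.6 use the same either-source wording at each visit. Protocol 14.3 and Appendix D then refer to these events with *and*, which suggests that *and* is loose shorthand for *or*. On that view no careful programmer would report the overlap. This stands as evidence of intent, and the overlap was probably not intended. But these passages govern which events are collected, not how the endpoint row is filled, and they support the fix.

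It is also true that the meaning of the Table 12 label is inferred, that SAP 8 presents the shells as changeable samples, and that their wording is loose in other places. The sample status does not reach SAP 5.2.2, which is body text with the same ambiguity.

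The limits on consequence stand in full. SAP 5.2.1 makes the secondary endpoints descriptive, no test or success criterion depends on the row, and SAP 5.3 and Table 12 still report SAEs by relatedness, including the combined figure.

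Finally, Protocol 14.2 allows a relationship of unknown, and Table 12 does not say where such events go. That is a separate gap and does not remove this one.

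**Conclusion.** The concern holds. The endpoint row shares its label with a block whose only non-redundant meaning is related to both, and nothing in the SAP directs the programmer elsewhere. Filled by label, the row would omit subjects whose related SAEs all have a single source. The understatement is confined to that row.

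On the TREVO counts the gap is at least 3.3 percentage points (5.0% against 8.3%, or about 10 against 17 subjects in 200), and larger with less overlap. This is an illustration, not an estimate for the registry: it comes from another study, where a committee and not the investigator adjudicated relatedness, and it rests on the assumptions stated with the calculation. The overlap in this registry is unknown. The point should be fixed, but its weight is limited because the endpoint is descriptive and the omitted events remain visible in Table 12.

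**What to change.** 1. In SAP 5.2.2, item 4, and in Table 11, define the endpoint as subjects with at least one SAE related to the study device or to the procedure through Day 90. State that it equals the total of Table 12's block "Study device or procedure related SAEs".
2. Because Protocol 5.2 and SAP 2.2.2 speak of rates, add two Table 11 rows: subjects with any device-related SAE, and subjects with any procedure-related SAE.
3. Rename the *and* blocks in Tables 12 and 13 so that they say related to both device and procedure.
4. Make the device block consistent. Table 12's heading is "Study device related SAEs only", but the row beneath it reads "Details of study device related SAEs", without the restriction. Table 13's device block has no such restriction at all.

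The cost is wording in the SAP and table shells. Both relationships are already recorded separately, so data collection does not change. The one drawback for the sponsor is that the reported rate may be higher than under the literal reading.

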# Stryker Neurovascular

**Document Title:** Trevo® Retriever Registry (China) Statistical Analysis Plan

**Document Number:** CDM10001420

**Ver AA**

**Table 12: All SAEs**

	# of events	Percentages of subjects with events* (Total subjects=xxx)
All SAEs		
Details of all SAEs	xx	xx.x% (xx/xxx)
...	xx	
...	xx	xx.x% (xx/xxx)
...	xx	xx.x% (xx/xxx)
Study device and procedure related SAEs		
Total	xx	xx.x% (xx/xxx)
Details of study device and procedure related SAEs	xx	xx.x% (xx/xxx)
...	xx	xx.x% (xx/xxx)
...	xx	xx.x% (xx/xxx)
...	xx	xx.x% (xx/xxx)
Study device related SAEs only		
Total	xx	xx.x% (xx/xxx)
Details of study device related SAEs	xx	xx.x% (xx/xxx)
...	xx	xx.x% (xx/xxx)
...	xx	xx.x% (xx/xxx)
...	xx	xx.x% (xx/xxx)
Procedure but not study device related SAEs		
Total	xx	xx.x% (xx/xxx)
Details of procedure but not study device related SAEs	xx	xx.x% (xx/xxx)
...	xx	xx.x% (xx/xxx)
...	xx	xx.x% (xx/xxx)
...	xx	xx.x% (xx/xxx)
Study device or procedure related SAEs		
Total	xx	xx.x% (xx/xxx)
Details of study device or procedure related SAEs	xx	xx.x% (xx/xxx)
...	xx	xx.x% (xx/xxx)
...	xx	xx.x% (xx/xxx)
Not study device and not procedure related SAEs		
Total	xx	xx.x% (xx/xxx)
Details of not study device and not procedure related SAEs	xx	xx.x% (xx/xxx)
...	xx	xx.x% (xx/xxx)
...	xx	xx.x% (xx/xxx)

\*: Some subjects may experience multiple events

STRYKER CONFIDENTIAL - THIS DOCUMENT CONTAINS CONFIDENTIAL AND PROPRIETARY INFORMATION THAT IS THE PROPERTY OF STRYKER CORPORATION. NEITHER THIS DOCUMENT NOR THE INFORMATION HEREIN MAY BE REPRODUCED, USED, OR DISCLOSED TO ANY THIRD PARTY WITHOUT THE PRIOR WRITTEN CONSENT OF STRYKER CORPORATION

# Stryker Neurovascular

**Document Title:** Trevo® Retriever Registry (China) Statistical Analysis Plan

**Document Number:** CDM10001420

**Ver AA**

**Table 13: All AEs during procedure**

	# of events	Percentages of subjects with events* (N=xxx)
Total AEs	xx	xx.x% (xx/xxx)
Details of AEs during procedure	xx	xx.x% (xx/xxx)
...	xx	xx.x% (xx/xxx)
...	xx	xx.x% (xx/xxx)
...	xx	xx.x% (xx/xxx)
Study device and procedure related AEs		
Total	xx	xx.x% (xx/xxx)
Details of study device and procedure related SAE	xx	xx.x% (xx/xxx)
...	xx	xx.x% (xx/xxx)
...	xx	xx.x% (xx/xxx)
...	xx	xx.x% (xx/xxx)
Study device related AEs		
Total	xx	xx.x% (xx/xxx)
Details of study device related AEs	xx	xx.x% (xx/xxx)
...	xx	xx.x% (xx/xxx)
...	xx	xx.x% (xx/xxx)
...	xx	xx.x% (xx/xxx)
Procedure but not study device related AEs		
Total	xx	xx.x% (xx/xxx)
Details of procedure but not study device related AEs	xx	xx.x% (xx/xxx)
...	xx	xx.x% (xx/xxx)
...	xx	xx.x% (xx/xxx)
...	xx	xx.x% (xx/xxx)
Study device or procedure related AEs		
Total	xx	xx.x% (xx/xxx)
Details study device or procedure related AEs	xx	xx.x% (xx/xxx)
...	xx	xx.x% (xx/xxx)
...	xx	xx.x% (xx/xxx)
Not study device and not procedure related AEs		
Total	xx	xx.x% (xx/xxx)
Details of not study device and not procedure related SAEs	xx	xx.x% (xx/xxx)
...	xx	xx.x% (xx/xxx)
...	xx	xx.x% (xx/xxx)

\*: Some subjects may experience multiple events

STRYKER CONFIDENTIAL - THIS DOCUMENT CONTAINS CONFIDENTIAL AND PROPRIETARY INFORMATION THAT IS THE PROPERTY OF STRYKER CORPORATION. NEITHER THIS DOCUMENT NOR THE INFORMATION HEREIN MAY BE REPRODUCED, USED, OR DISCLOSED TO ANY THIRD PARTY WITHOUT THE PRIOR WRITTEN CONSENT OF STRYKER CORPORATION

## Stryker Neurovascular

**Document Title:** Trevo® Retriever Registry (China) Statistical Analysis Plan

**Document Number:** CDM10001420

**Ver AA**

**Table 14: Device Malfunction**

	# of events	Percentages of study devices with events* (Total device=xxx)	Percentages of subjects with events** (Total subjects=xxx)
Total	xx	xx.x% (xx/xxx)	xx.x% (xx/xxx)
Details of device malfunction	xx	xx.x% (xx/xxx)	xx.x% (xx/xxx)
...	xx	xx.x% (xx/xxx)	xx.x% (xx/xxx)
...	xx	xx.x% (xx/xxx)	xx.x% (xx/xxx)
...	xx	xx.x% (xx/xxx)	xx.x% (xx/xxx)

\*: One device may have multiple malfunctions  
\*\*: One subject may have multiple devices with malfunctions

STRYKER CONFIDENTIAL - THIS DOCUMENT CONTAINS CONFIDENTIAL AND PROPRIETARY INFORMATION THAT IS THE PROPERTY OF STRYKER CORPORATION. NEITHER THIS DOCUMENT NOR THE INFORMATION HEREIN MAY BE REPRODUCED, USED, OR DISCLOSED TO ANY THIRD PARTY WITHOUT THE PRIOR WRITTEN CONSENT OF STRYKER CORPORATION
